5.4.13.1 Possible Drug Interactions

Pozotinib is a substrate for cytochrome P450 (CYP) 3A4 and 2D6 enzymes. Patients may be taking medications that are strong inhibitors or inducers of these two enzymes ([Table 2](#)). The plasma concentration of pozotinib could be different in these patients. The Investigator should try to substitute a medication that is not a strong inhibitor/inducer of these enzymes, if possible. If there is not an available substitute for a medication that a patient is taking, or the patient is not willing, to change medications, the Investigator must monitor the patient closely for possible AEs or changes in response.

Pozotinib is also a moderate inhibitor of CYP2C8 and CYP2D6; patients who take medications that are sensitive substrates for these two enzymes ([Table 2](#)) should be followed closely for possible changes in the patient's response to these medications. Patients should be told to avoid grapefruit juice, Seville oranges, and St. John's Wort during the study treatment.

Table 2 Examples of Important Clinical Inhibitors/Inducers/Substrates for P450 Enzymes Involved in the Metabolism of Pozotinib

CYP	Strong Inhibitor	Strong Inducer	Sensitive Substrate
2D6	Bupropion, Fluoxetine, Paroxetine, Quinidine, Terbinafine	None	Atomoxetine, Desipramine, Dextromethorphan, Eliglustat, Nebivolol, Nortriptyline, Perphenazine, Tolterodine, Venlafaxine
3A4	Boceprevir*, Cobicistat, Conivaptan*, Danoprevir* and Ritonavir, Elvitegravir* and Ritonavir, Grapefruit Juice, Indinavir** and Ritonavir, Itraconazole, Ketoconazole, Lopinavir and Ritonavir, Paritaprevir / Ritonavir / Omibitasvir** + Dasabuvir*, Posaconazole*, Ritonavir, Saquinavir** and Ritonavir, Telaprevir**, Tipranavir* and Ritonavir, Troleandomycin*, Voriconazole	Carbamazepine, Enzalutamide, Mitotane, Phenytoin, Rifampin, St. John's Wort	Not Applicable
2C8	Not Applicable	Not Applicable	Repaglinide

Source:

<https://www.fda.gov/drugs/developmentapprovalprocess/developmentresources/druginteractionslabeling/ucm093664.htm>

*: Not approved in Japan

**: Withdrawn from Japanese market

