Because Phase 1 is for DLT assessment and dose finding, pozotinib dose modifications are not permitted during Cycle 1 in Phase 1. Dose modifications are permitted beginning with Cycle 2

[figure not shown]
based on Sponsor recommendations. Patients who discontinue from the study for reasons other than DLTs will be replaced.

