4.2 Exclusion Criteria

1. **Phase 2 :** Patient has EGFR T790M mutation or any other acquired EGFR exon 20 point mutation
2. **Phase 2 :** Patient has had previous treatment with poziotinib. The currently approved TKIs that are not considered to be exon 20 insertion-selective are permissible.
3. Patient is concurrently receiving chemotherapy, biologics, immunotherapy for cancer treatment; systemic anti-cancer treatment or investigational treatment should not be used within 2 weeks prior to Cycle 1, Day 1; local radiation therapy for bone pain may be allowed.
4. Patient has used strong inhibitors/inducers of CYP3A4 and CYP2D6 within 1 month prior to Cycle 1, Day 1.
5. Patient has brain metastases and is clinically symptomatic, requires high dose or increasing doses of systemic corticosteroids, or needs any anticonvulsant therapy for metastatic brain disease.
6. Patient has a high risk for or history of congestive heart failure (CHF) Class III/IV according to the New York Heart Association (NYHA) Functional Classification or serious cardiac arrhythmias requiring treatment. Cardiac ejection fraction $<50\%$ as determined by either echocardiogram (ECHO) or multi-gated acquisition (MUGA) during Screening.

7. Patient has had another primary malignancy within 3 years prior to starting study treatment, except for adequately treated basal or squamous cell carcinoma of the skin or cancer of the cervix in situ
8. Patient is confirmed to have clinically significant or recent acute gastrointestinal disease presenting as diarrhea and/or coloenteritis as a main symptom (ie, acute enteritis, malabsorption, or Common Terminology Criteria for Adverse Events (CTCAE, version 5.0) Grade 2 or above diarrhea due to other etiologies)
9. Patient has an active Grade ≥ 2 skin disorder, rash, mucositis, or skin infection that needs medication or therapy or existing Grade ≥ 2 skin toxicity from previous therapies; Grade > 2 neuropathy, Grade ≥ 2 pneumonitis.
10. Patient is unable to take drugs orally due to disorders or diseases that may affect gastrointestinal function, such as inflammatory bowel diseases (eg, Crohn's disease, ulcerative colitis) or malabsorption syndrome, or procedures that may affect gastrointestinal function, such as gastrectomy, enterectomy, or colectomy

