5.4.13 Concomitant Medications

All medications administered from Screening to the Safety Follow-up Visit will be recorded on the CRF. A concomitant medication is any medication a patient is using from Cycle 1, Day 1 to the Safety Follow-up Visit. Pozotinib is not considered a concomitant medication.

All concomitant medications recorded at study entry must have a related, ongoing concomitant illness listed under the medical history at the time of patient entry into the trial. Patients may continue to use any ongoing medications not prohibited by the protocol.

All prescription and over-the-counter medications at trial entry as well as any new medications started during the trial must be documented on the CRF and in the source documents. The documentation should continue until 35 (± 5) days after the last dose of pozotinib.

Premedications (such as antiemetics) used for supportive care are allowed as per institutional standards or guidelines and Investigator discretion.

Other supportive and palliative therapies may be allowed during the study upon prior authorization from Sponsor's Medical Monitor.

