5.4.13.2 Premedication and Supportive Treatment

Pre-medications, as per Institutional standard of care as determined by the Investigator, should be administered before pozotinib on **Day 1**. All supportive medications for potential diarrhea and rash management should be distributed to the patient on **Day 1** with instructions on their use. During Cycle 1, use of growth factors is not allowed in the dose-finding phase of the study.

Preliminary information from **Cohort 1** in SPI-POZ-202 suggest that dose interruptions should be minimized in order to reduce the risk of progression. Supportive medications, including early steroid use, should be considered even in the presence of low-grade “on-target” toxicity (eg, rash, diarrhea).

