5.4.13.3 Uses of Warfarin or Other Similar Anticoagulants

Warfarin or other similar anticoagulants should be used cautiously during treatment with pozotinib. When it cannot be avoided, regular monitoring of INR is required and prior authorization from the Sponsor’s Medical Monitor is required.

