5.4.14 Patient Discharge

All patients in the Phase 1 dose-finding phase will be hospitalized for at least 14 days from Cycle 1, Day 1 of the study. In order to be discharged from the hospital, the patient must not have any ongoing SAEs or DLTs, and in the Investigator's judgement, the patient is healthy enough to be discharged. At the discretion of the Investigator, the patient may continue to be hospitalized after Day 14 if in his or her clinical judgement this would be in the best interest of the patient. Hospitalization may continue for as long as medically necessary. Prior to patient discharge, the evaluations described in Section 5.3.3 of the protocol will be performed to assess and document the patient's readiness to be discharged according to the criteria in Section 5.3.4.

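### No class rule restricts strong CYP3A4/CYP2D6 inhibitors or inducers newly started in Phase 1 Cycle 1, when the pozotinib dose cannot be changed

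*Combined protocol and SAP*

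**What the plan says.** Before treatment, exclusion criterion 4 (Section 4.2 and synopsis, both phases) is a bar: "Patient has used strong inhibitors/inducers of CYP3A4 and CYP2D6 within 1 month prior to Cycle 1, Day 1".

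On treatment, Section 5.4.13.1 takes a different line. It says that patients may be on strong inhibitors or inducers of these enzymes and that the pozotinib concentration "could be different in these patients". It asks the investigator to try to substitute. If no substitute exists, "or the patient is not willing, to change medications, the Investigator must monitor the patient closely for possible AEs or changes in response". Patients are also told to avoid grapefruit juice, Seville oranges and St. John's Wort. The section does not distinguish by phase or cycle, and the list of prohibited therapies (Section 5.4.13.6) covers anti-cancer and experimental treatment only.

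Section 3.1.1 states that "pozotinib dose modifications are not permitted during Cycle 1 in Phase 1".

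The protocol is stricter for other drugs:
- Warfarin and similar anticoagulants (5.4.13.3): "When it cannot be avoided, regular monitoring of INR is required and prior authorization" from the Medical Monitor.
- Growth factors (5.4.13.2): "During Cycle 1, use of growth factors is not allowed in the dose-finding phase of the study".

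**The concern.** Cycle 1 of Phase 1 is where the MTD or MAD is decided. A strong inhibitor or inducer started in that cycle could change exposure to pozotinib at a nominally fixed dose. A DLT, or the absence of one, would then partly reflect the other drug. The dose cannot be adjusted to compensate, and each level holds only 3 to 6 patients, so one patient can decide whether the level is passed. The selected dose goes on to 40 Phase 2 patients.

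Against that, the written standard for continuing such a drug is low. A patient's preference is enough, no approval step is named, and nothing directs the dose-finding meeting to identify such a patient.

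**Working it through.** No planned figure is at issue, so the check is a reading of the text followed by an illustration.

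**Which patients does the gap cover?** Criterion 4 and Section 5.4.13.1 do not fit together well. The first excludes recent users; the second speaks of patients who may be using these drugs and may not want to change, which describes ongoing medication. Read together, a patient already on such a drug should not reach Cycle 1. That leaves a drug newly started in Cycle 1, or use that screening missed. For these, the only restrictions found are the advice on grapefruit juice, Seville oranges and St. John's Wort, and the Appendix 4 advice to consider other steroids in place of dexamethasone.

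**How many drugs are involved?** Table 2, which gives examples only, lists 5 CYP2D6 inhibitors, 18 CYP3A4 inhibitor entries and 6 CYP3A4 inducers: 5 + 18 + 6 = 29. Of these, 11 are marked as not approved in, or withdrawn from, Japan, and patients are told to avoid 2 more: 29 - 11 - 2 = 16. Removing three HIV agents (HIV exclusion) and two anti-cancer agents (Section 5.4.13.6) leaves 11.

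**How much could one affected patient move a dose decision?** Assumptions, none from the documents:
- Standard 3+3 applied mechanically (Figure 12 is not shown): escalate on 0/3, or on 1/3 followed by 0/3.
- True DLT probability p; exactly one of the first three patients has probability a instead.
- DLT hazard spread evenly over 28 days.

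Formulas:
- P(0/3) = (1-p)²(1-a)
- P(1/3) = a(1-p)² + (1-a)·2p(1-p)
- P(escalate) = P(0/3) + P(1/3)·(1-p)³
- Risk doubled on Days 15-28 only: a = 1 - √[(1-p)(1-2p)]
- Risk halved on Days 15-28 only: a = 1 - √[(1-p)(1-p/2)]
- Risk doubled for the whole cycle: a = 2p

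Worked case, p = 0.2, doubled on Days 15-28: a = 1 - √(0.8 × 0.6) = 0.307; P(0/3) = 0.64 × 0.693 = 0.443; P(1/3) = 0.307 × 0.64 + 0.693 × 0.32 = 0.418; P(escalate) = 0.443 + 0.418 × 0.512 = 0.658, against 0.512 + 0.384 × 0.512 = 0.709 with nobody affected.

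| P(escalate) | p = 0.1 | p = 0.2 | p = 0.3 |
|---|---|---|---|
| Nobody affected | 0.906 | 0.709 | 0.494 |
| Doubled, Days 15-28 | 0.888 | 0.658 | 0.415 |
| Halved, Days 15-28 | 0.915 | 0.732 | 0.528 |
| Doubled, whole cycle | 0.871 | 0.613 | 0.354 |

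Given one affected patient, escalation is 1.8, 5.1 and 8.0 points less likely (doubled, Days 15-28), 0.9, 2.3 and 3.3 points more likely (halved), or 3.5, 9.5 and 14.0 points less likely (doubled, whole cycle).

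**On average.** If a share q of patients is affected, exactly one of three is affected with probability 3q(1-q)²: 0.058 at q = 0.02 and 0.135 at q = 0.05 (assumed range). The average fall for Days 15-28 runs from 1.81 × 0.058 = 0.10 to 7.96 × 0.135 = 1.08 points, and for the whole cycle from 3.51 × 0.058 = 0.20 to 13.98 × 0.135 = 1.89 points.

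**The case against.** The strongest reply is that the plan already contains most of the risk.

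- **Entry.** A reader might infer from Section 5.4.13.1 that a patient already on a strong inhibitor who declines to change can simply enter the DLT window. The documents do not support that: criterion 4 applies in Phase 1 and should exclude this patient.
- **Days 1-14.** Patients are "hospitalized for at least 14 days from Cycle 1, Day 1 of the study", so a new prescription should be seen, and intensive PK on Days 1 and 13 (5.4.8) would describe exposure.
- **Days 15-28.** Discharge requires adverse events at Grade 1 or below, or at baseline, and no ongoing SAE (5.3.4). Those who go home are therefore well. They have 24-hour physician contact and a Day 22 call that covers concomitant medication. A potentially drug-related Grade 3 or higher event triggers a PK sample.
- **Attribution.** Causality grading considers concomitant medications (Table 4). The Medical Monitor assesses DLTs, and dose decisions use all safety information (3.1.1, 7.1).
- **Other routes.** Section 5.4.13 says "Other supportive and palliative therapies may be allowed during the study upon prior authorization" from the Medical Monitor, which may catch some new drugs. The investigator or sponsor can withdraw a patient (4.3), and those who leave before completing Cycle 1 for non-DLT reasons are replaced (8.1).
- **Size.** The illustration takes the drug to start on Day 15 with full effect at once. Spreading starts evenly over Days 15-28 cuts the falls to 0.9, 2.6 and 4.2 points, and the average to 0.05-0.56.

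Most of this stands, and it keeps the point small. What it does not supply is a rule on the drugs themselves: none of these safeguards restricts the class in Cycle 1 or removes unwillingness as a sufficient reason. Handling of affected data might be set out in the separate SAP or the PK analysis plan, which are not available here. Section 8 requires the PK plan only before database lock, so it need not exist when doses are chosen.

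**Conclusion.** The gap is real but narrow: a strong CYP3A4/CYP2D6 inhibitor or inducer newly started, or missed at screening, in Phase 1 Cycle 1. Few patients are likely to be affected. Under the stated assumptions, one affected patient lowers the chance of escalating by about 2 to 8 points if risk doubles on Days 15-28, with 14 points as the largest value under doubling for the whole cycle. Averaged over an assumed 2-5% frequency, the Days 15-28 fall is about 1 point or less.

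A reader might go further and conclude that the MTD will be biased in a known direction. The documents do not support that. They give no interaction size, and inducers could act the opposite way to inhibitors. Direction is unclear even for CYP2D6 inhibitors: that enzyme forms M2, whose in vitro EGFR activity is nearly identical to the parent's, and Section 1.1.2.6 suggests that parent plus M2 may best reflect toxicity. Blocking it could raise one and lower the other.

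This is a cheap improvement to safety and to DLT attribution, of low severity; it does not undermine the dose-finding design.

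**What to change.** Add to Section 5.4.13.1: during Phase 1 Cycle 1, strong CYP3A4/CYP2D6 inhibitors and inducers are not permitted unless medically unavoidable, and then only with Medical Monitor prior authorization, as already required for warfarin. Patient unwillingness to change is not sufficient.

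If one is used, flag the patient at the existing dose-finding meeting (7.1) before the dose decision. Keep any DLT in the count. Mark that patient's Day 13 PK profile if the drug was started by Day 13. The flag should be descriptive only: dropping the patient from the count could leave 2 of 3 evaluable with no rule for deciding the dose.

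Cost: a short addition to one section, one item at a meeting already planned, and a flag drawn from concomitant medication data already recorded. The downside is slightly restricted prescribing in Cycle 1.

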5.4.13.2 Premedication and Supportive Treatment

Pre-medications, as per Institutional standard of care as determined by the Investigator, should be administered before pozotinib on **Day 1**. All supportive medications for potential diarrhea and rash management should be distributed to the patient on **Day 1** with instructions on their use. During Cycle 1, use of growth factors is not allowed in the dose-finding phase of the study.

Preliminary information from **Cohort 1** in SPI-POZ-202 suggest that dose interruptions should be minimized in order to reduce the risk of progression. Supportive medications, including early steroid use, should be considered even in the presence of low-grade “on-target” toxicity (eg, rash, diarrhea).

5.4.13.3 Uses of Warfarin or Other Similar Anticoagulants

Warfarin or other similar anticoagulants should be used cautiously during treatment with pozotinib. When it cannot be avoided, regular monitoring of INR is required and prior authorization from the Sponsor’s Medical Monitor is required.

5.4.13.4 Other Anticancer Therapies

No additional cytotoxic agents, biologic therapy, or immune response modifiers for cure-intent purpose are to be administered to patients until study treatment has been discontinued.

5.4.13.5 Drugs that Affect Gastric pH

In vitro studies have shown that the solubility of pozotinib is pH dependent. Pozotinib is highly soluble at acidic pH, its solubility is significantly reduced at neutral or basic pH. Although the effect of pH on systemic exposure of pozotinib has not been established, based on the solubility profile, it is quite likely that the absorption of pozotinib could be lower at higher pH.

Because proton pump inhibitors (PPIs), H2 histamine receptor antagonists and antacids increase the gastric pH, we recommend that if possible, concomitant administration of long-acting PPIs or H2 receptor antagonists with pozotinib should be avoided, which is similar to the instructions for other TKIs. If needed, patients may take short-acting antacids (e.g., Maalox[®]) at least 4 hours before or after pozotinib administration. Patients should also avoid drink water that is alkaline.

5.4.13.6 Prohibited Therapies or Medications

No other anti-cancer therapy, including chemotherapy, radiation therapy, immunotherapy, or experimental medications, are permitted during the trial. Any disease progression that requires anti-tumor therapy will be cause for discontinuation from the study

5.4.14 Patient Discharge

All patients in the Phase 1 dose-finding phase will be hospitalized for at least 14 days from Cycle 1, Day 1 of the study. In order to be discharged from the hospital, the patient must not have any ongoing SAEs or DLTs, and in the Investigator's judgement, the patient is healthy enough to be discharged. At the discretion of the Investigator, the patient may continue to be hospitalized after Day 14 if in his or her clinical judgement this would be in the best interest of the patient. Hospitalization may continue for as long as medically necessary. Prior to patient discharge, the evaluations described in Section 5.3.3 of the protocol will be performed to assess and document the patient's readiness to be discharged according to the criteria in Section 5.3.4.

6 STUDY DRUG AND PHARMACEUTICAL INFORMATION

6.1 Pozotinib

Pozotinib will be supplied by Spectrum.

6.2 Pozotinib Composition

The pozotinib drug substance is a hydrochloride salt of pozotinib and is formulated as a tablet for oral administration.

6.3 Pozotinib Supply and Labeling

Pozotinib tablets are supplied in 2.0-mg and 8.0-mg dose strengths.

6.4 Pozotinib Storage and Handling

Pozotinib supplies must be stored in a secure, limited-access location under the storage conditions specified on the drug supply label.

KEEP THIS AND ALL MEDICATIONS OUT OF THE REACH OF CHILDREN.

6.5 Pozotinib Administration

Pozotinib should be taken with food and a glass of water (approximately 240 mL) at approximately the same time(s) each day.

Once a Day Dosing:

- **Phase 1, Days 1 to 14:** Patients will be administered pozotinib every 24 (± 1) hours
- **Phase 1 post-Hospitalization and Phase 2:** If the daily dose is missed, this dose may be administered any time during the day, but at least 8 hours prior to the next scheduled dose.

Twice a Day Dosing:

- **Phase 1, Days 1 to 14:** Patients will be administered pozotinib every 12 hours (± 30 minutes)
- **Phase 1 post-Hospitalization and Phase 2:** The first dose should be taken in the morning and the second dose should be taken approximately 8 to 12 hours later. If a dose is missed, and there is less than 8 hours before the next scheduled dose, the dose should be skipped and the next dose taken as scheduled.

6.6 Diarrhea Management

Tyrosine kinase inhibitors may cause diarrhea when taken. Prophylaxis for this is strongly encouraged and may be addressed by the Investigator using the Institute's standard of care. Any prophylaxis treatment will be recorded in the CRF and the source documents.

6.7 Pozotinib Dose Modification Recommendations

In Phase 1 of the study (Dose-Finding), dosing modifications are not allowed during Cycle 1 but are allowed beginning with Cycle 2. Dosing modifications are allowed at any time during Phase 2 of the study. Dosing modifications are described in [Table 3](#). If needed, doses will be reduced by 2 mg/dose (i.e., if on QD, the reduction will be a total of 2 mg/day or if on BID, the reduction will be a total of 4 mg/day), regardless of starting dose, and will be at the Investigator's discretion; the Sponsor should be notified. Dose modifications not described in the table below must be discussed with Medical Monitor for approval. After dose reductions, if the patient has a documented confirmed progression, the patient's dose can be increased up to the starting dose.

Table 3 Recommendations for Dose Reductions after Cycle 1 in Phase 1 and During Phase 2

Related Adverse Event	Triggering Criteria	First Occurrence	Subsequent Occurrences
Diarrhea	Grade ≥ 3 (Despite optimal anti-diarrhea management)	Stop pozotinib treatment until the AE has improved to Grade ≤ 1 and then continue treatment at the same dose. or Reduce Pozotinib Dose by 2 mg/dose	Reduce pozotinib dose by 2 mg/dose
	Grade ≥ 2 for ≥ 48 hours (Despite optimal diarrhea management)		
Rash	Grade ≥ 3 (Despite adequate anti-rash management)		
Fatigue	Grade ≥ 3		
Mucositis/ Stomatitis	Grade ≥ 3 (Despite optimal management)		
Nausea and/or Vomiting	Grade ≥ 3 (Despite optimal anti-emetics)		
	Grade ≥ 2 for ≥ 48 hours (Despite optimal anti-emetics)		
Rash	Any Grade	Refer to Appendix 4	
LVEF Dysfunction	Grade ≥ 3	Discontinue Treatment	NA
Pneumonitis	Grade 1	Stop pozotinib treatment, assess pulmonary function, and monitor the patient as clinically indicated. Contact the Sponsor to discuss continuing treatment, if resolved.	Discontinue Treatment
	Grade ≥ 2	Discontinue treatment. Assess pulmonary function and monitor the patient as clinically indicated.	NA

Abbreviation: NA = not applicable.

Dose interruptions should be minimized in order to reduce the risk of progression. Supportive medications, including early steroid use, should be considered even in the presence of low-grade “on-target” toxicity (eg, rash, diarrhea). The respiration and pulmonary function of the patient will be assessed throughout Cycle 1. Interstitial lung disease (ILD) is a clinical diagnosis and if in the opinion of the Principal Investigator the patient has developed signs or symptoms of Grade ≥ 2 pneumonitis (CTCAE Version 5.0), the patient would stop dosing and depending on the response/recovery may be discontinued from the study. If the patient has developed signs or symptoms of Grade 1 pneumonitis, the Investigator can stop treatment after consultation/discussion with the Medical Monitor.

